Specific Aim 1: Integrate the My Recovery Plan tool and existing PS tools and strategies to develop a manualized intervention called Recovery Bridge for use by VA PS working to help Veterans make the transition from acute inpatient psychiatric hospitalization to community living.

Specific Aim 2: Complete an open pilot trial (n=15) to examine the feasibility, fidelity, and acceptability of the Recovery Bridge intervention in relation to well specified benchmarks supporting continued and expanded investigation

Specific Aim 3: As part of the open pilot trial: 1) explore the impact of the intervention on readmission rates (at 30 and 90 days), and connection to outpatient care compared to a control group (n of up to 60) identified from administrative data, and; 2) explore the change in recovery and Quality of Life measures over time in the intervention participants.

2 \* Discuss the research design including but not limited to such issues as: probability of group assignment, potential for subject to be randomized to placebo group, use of control subjects, etc.:  
 This is a feasibility and acceptability pilot study and all Veteran participants will receive the intervention; no human subjects control or placebo group will be used.

3 \* Describe the relevant prior experience and gaps in current knowledge. Describe any relevant preliminary data:  
 More knowledge and evidence is needed regarding the use of peer facilitated interventions that support the transition from inpatient mental health hospitalization to living in the community.

As such the overarching purpose of the current study is to optimize existing materials to develop a manualized transitional discharge intervention called Recovery Bridge. The study will also complete an open trial and collect qualitative interview data from a range of stakeholders to examine preliminary outcomes and inform future research to more broadly disseminate and implement the Recovery Bridge Intervention.

4 \* Provide the scientific or scholarly background, rationale, and significance of the research and how it will add to existing knowledge:

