The time following discharge from psychiatric hospitalization is a high-risk period and has been associated with a range of negative outcomes including high rates of hospital readmission and suicide. Among Veterans at high risk for suicide who are discharged from inpatient psychiatric care, 30% are readmitted within one year. Even more alarmingly, among Veterans who are high psychiatric service users, 79.8% of Veterans are readmitted to psychiatric inpatient units within two years of discharge. The VHA has made concerted efforts to increase outpatient follow-up within 7 days of psychiatric discharge; in fact, seven-day follow-up rates increased from 39% to 75% between 2005 and 2010. Unfortunately, this increase had no impact on 90-day psychiatric readmission rates. Recent survey data indicate that over two thirds of Veterans discharged from psychiatric inpatient units are not receiving their preferred type of care during post-hospitalization follow-up, with support from a Veteran peer specifically named as a preferred service. These data indicate that different and more effective interventions are needed at this critical care transition.

There is some empirical support for the effectiveness of selected interventions for reducing psychiatric hospital readmission, but the evidence is limited. Two recent systematic reviews/meta-analyses summarize this broad yet extremely heterogeneous literature. The general consensus is that interventions that involve making contact with service users after discharge (e.g., letters) or introducing new roles to oversee aspects of the discharge process are not effective in reducing rates of readmission. Interventions that provide psychoeducation to service users and/or family members may improve some service-level outcomes such as readmission. The conclusions were mixed on the potential effectiveness of interventions that aim to bridge the boundaries between the hospital and community (e.g., Critical Time Intervention, Transitional Discharge Model), though an emphasis on a strong therapeutic relationship with a consistent provider across the care transition may be critical. Although psychoeducation and strong rapport with a therapeutic support person appear to be important, additional high-quality research is required to definitively establish the effectiveness of transitional discharge interventions that rely on these strategies.

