The active sample (n=15) will be compared to a randomly selected contemporaneous (or near-contemporaneous) group-matched sample (n of up to 60) from administrative data on a couple of post-discharge metrics. The first is the SAIL post-discharge engagement metric of 3 outpatient visits within 30 days (or if flagged for suicide risk, 4 outpatient visits within 30 days). The second metric will be whether the patient is re-admitted to in-patient psychiatric hospitalization within 30 days. Matching will be based on diagnostic grouping, age group, and gender. In addition to descriptive statistics (proportions by group), matched pairs analyses (McNemar's test and matched-pairs OR's with 95% confidence intervals) will be used to compare the active sample to the administrative sample on (1) proportion meeting the post-discharge engagement metric, and (2) proportion with inpatient re-hospitalization within 30 days. These analyses are exploratory given limited power and precision of 95% confidence intervals. All quantitative study data will be password protected and stored in a VA REDCap database

Qualitative Analyses: For qualitative data, we will utilize a rapid analysis summary approach. To begin, we will create a summary template with deductively identified key domains (or topics) of interest. We will iteratively refine the summary template by independently summarizing the first few transcripts and then meeting as a team to discuss the summaries, establish agreement, and revise the template with inductively identified domains. When the template is finalized, each of the remaining transcripts will be summarized by an individual and audited by a second person, with disagreements brought to the larger team for discussion. Data from the summaries will be entered into a matrix to begin analysis and identification of common themes. Utilizing this rapid approach will allow us to quickly and efficiently assess the data for the primary outcome of acceptability.

ID: VIEW4E02806052800  
Name: v2\_Sample Size and Data Analysis

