## Recruitment

1 \* Describe plans for recruitment, including the identification of potential participants (or acquisition of charts/records/samples) and initial interactions with them: (If this study involves the VA please list all sites at which recruitment will take place.):  
Veteran Participants:  
Potential participants will be patients on the Baltimore VAMC inpatient psychiatry unit (commonly referred to as the 6A unit). Our research staff will monitor the census of the inpatient unit every day and recruit Veterans as early as possible during their stay. Our study staff will work closely with the staff that works on the 6A unit. Participants will be identified by two methods: (1) CPRS chart review and screening of the 6A unit census via use of partial HIPAA waiver, (2) VA clinician referrals, from those who work on the 6A unit, of participants who meet inclusion criteria and who might be interested in participating. No cold calling of Veterans would take place.

Prior to research staff contact with potential Veteran, 6A staff will mention the study to Veterans who meet inclusion criteria to gauge an initial interest. Study staff may also inquire about Veterans on the 6A census via CPRS to see if the 6A staff would recommend, and then 6A staff will mention the study to the Veteran.

If the Veteran expresses interest, 6A staff will inform study staff that the Veteran is open to a phone call. Initial contact with Veterans would then be made via the phone on the 6A unit. Study staff may use provided script to call the Veteran on the 6A unit phone to describe the study and schedule a consent session to take place in person. Study staff can also approach Veterans while on the unit to explain the study, and allow ample time for questions and evaluation of capacity to provide consent (a consent appointment). Those consented will be asked to complete a brief (20-30 min) assessment including measures of the outcomes noted below. The two PS working on the project will also be available to meet the Veteran during the recruitment and assessment process to help establish and build rapport.

Research assistants who will interact with participants are all specially trained to work with persons with mental illnesses. Research staff will first consult the participant's treatment team for permission to begin the consent process. This will help avoid approaching people who may be in crisis or may not be able to comprehend the study procedures, risks, and benefits.

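### The administrative controls are not matched on prior psychiatric admission, so the exploratory 30-day readmission contrast can partly reflect admission history, in either direction

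*Combined protocol and SAP*

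**What the plan says.** Specific Aim 3 (Justification, Objective, & Research Design, item 1) is to "explore the impact of the intervention on readmission rates (at 30 and 90 days), and connection to outpatient care compared to a control group". Sample Size and Data Analysis, item 2, describes the controls as a "randomly selected contemporaneous (or near-contemporaneous) group-matched sample (n of up to 60) from administrative data". The list of factors follows: "Matching will be based on diagnostic grouping, age group, and gender". One of the two outcomes is "whether the patient is re-admitted to in-patient psychiatric hospitalization within 30 days". The analysis is proportions by group, McNemar's test and matched-pairs odds ratios. No covariate adjustment is mentioned, and the only limitations named are power and precision.

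The background (same Justification section, item 4) reports that "among Veterans who are high psychiatric service users, 79.8% of Veterans are readmitted to psychiatric inpatient units within two years of discharge".

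The active Veterans reach the study by a different route. Under Recruitment, item 1, research staff screen the unit census and charts, or unit clinicians refer. Unit staff raise the study with the Veteran before research contact, and "Study staff may also inquire about Veterans on the 6A census via CPRS to see if the 6A staff would recommend". The treatment team must then agree before consent starts, and the Veteran must be interested. Recruitment, item 2, and Informed Consent Process, items 2 and 7, add comprehension questions that must be answered correctly within two attempts.

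**The concern.** Matching is the only control for confounding that this comparison has. It leaves out a characteristic that the protocol itself presents as marking a group with high readmission. The route into the active group can also shift how common that characteristic is. A Veteran in crisis, unwilling, or unable to answer the comprehension questions does not enter the active group, but a similar Veteran can be drawn as a control. Two people of the same diagnostic group, age group and gender can differ widely in past admissions, so the three factors do not remove the difference.

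At stake is how the readmission odds ratio is read. If recent admissions are rarer among the 15 than among the controls, an ineffective intervention looks protective. If they are commoner, a useful one looks inert or harmful. The stated caveat does not cover this, because limited power and precision describe random error. A wide interval neither reveals nor removes a systematic difference between the groups.

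**Working it through.** The plan gives no effect size, power figure or expected readmission rate for this contrast, so there is no figure of its own to reproduce. The check is whether the bias can be sized from the documents and, if not, how it compares with random error.

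**Step 1: the formula.** Suppose the intervention does nothing. Let *h* be the 30-day readmission risk in Veterans with a heavy admission history and *l* the risk in the rest. Let *a* and *c* be the shares with that history among active and control Veterans. Expected risk is *a·h* + (1 − *a*)·*l* in the active group and *c·h* + (1 − *c*)·*l* in controls. The spurious difference is (*a* − *c*)·(*h* − *l*).

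**Step 2: what the documents supply.**
- *h*: only 79.8% over two years, with no 30-day figure.
- *l*: nothing. No rate is given for Veterans who are not high users.
- *a* and *c*: nothing.

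The bias therefore cannot be derived. It is zero if *a* = *c*, and its sign follows the sign of *a* − *c*, which is unknown.

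**Step 3: an assumed range.** All inputs in this table are assumptions.

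| *h* / *l* | *a* / *c* | Active vs control risk | Difference (points) | Odds ratio |
|---|---|---|---|---|
| 15% / 5% | 10% / 30% | 6.0% vs 8.0% | −2.0 | 0.73 |
| 15% / 5% | 10% / 50% | 6.0% vs 10.0% | −4.0 | 0.57 |
| 20% / 8% | 10% / 30% | 9.2% vs 11.6% | −2.4 | 0.77 |
| 20% / 8% | 10% / 50% | 9.2% vs 14.0% | −4.8 | 0.62 |
| 25% / 8% | 10% / 30% | 9.7% vs 13.1% | −3.4 | 0.71 |
| 25% / 8% | 10% / 50% | 9.7% vs 16.5% | −6.8 | 0.54 |
| 30% / 10% | 10% / 30% | 12.0% vs 16.0% | −4.0 | 0.72 |
| 30% / 10% | 10% / 50% | 12.0% vs 20.0% | −8.0 | 0.55 |

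Second row written out: 0.10 × 15 + 0.90 × 5 = 6.0; 0.50 × 15 + 0.50 × 5 = 10.0; odds ratio (0.06/0.94)/(0.10/0.90) = 0.57. Swapping *a* and *c* reverses each difference and inverts each odds ratio, giving +2 to +8 points and odds ratios from 1/0.77 = 1.30 to 1/0.54 = 1.85.

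**Step 4: random error.** With 15 and 60 Veterans, ignoring the matching, the approximate 95% half-width for a difference is 1.96 × √[*p*(1 − *p*)(1/15 + 1/60)]. This is 9.7 points at *p* = 3%, 12.3 at 5%, 17.0 at 10% and 20.2 at 15%. One readmission moves the active proportion by 1/15 = 6.7 points. The normal approximation is rough at these counts, but random error exceeds every bias in the table.

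**The case against.** The strongest reply is that this is an unpowered pilot, Aim 3 only sets out to explore, the analysis is labelled exploratory, and no stated decision rests on the contrast. With noise larger than the likely bias, better matching will not make the result informative. This stands as far as weight goes: the point does not touch feasibility or acceptability. It does not excuse the omission, since the label rests on imprecision alone and the plan still intends to report odds ratios with confidence intervals.

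Two documents that could restrict the groups are not available here: the companion administrative-data protocol (HP-00110495) and the Veteran eligibility checklist. That is a fair reservation, but the analysis section gives its three factors without pointing to others.

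A reader might also infer three stronger things that the documents do not support.

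- *A 2.2-fold risk gradient by service history.* The background also says "Among Veterans at high risk for suicide who are discharged from inpatient psychiatric care, 30% are readmitted within one year". Under constant hazards this gives −ln(0.70) = 0.357 per year, against −ln(0.202)/2 = 0.800 for high users, a ratio of 2.24. But the 30% belongs to Veterans at high suicide risk, not to low users, so the ratio does not measure this confounder.
- *That unit staff hand-pick participants by history.* Research staff screen the census and charts themselves, a staff recommendation is something they may ask for, and the flyer (Advertising Detail) invites Veterans to call. The treatment team's permission is meant to protect people in crisis or unable to follow the study. No step is said to work on past admissions. Any link to them is inferred.
- *That past outpatient contact confounds the engagement metric in the same way.* No section ties prior attendance to that metric, and Prospective Data, item 2, lists encounters after discharge, not before. Matching on prior outpatient visits is not warranted on this evidence.

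**Conclusion.** The concern holds for the 30-day readmission contrast. As written, the plan leaves a risk marker named in its own background unmatched and unadjusted, while entry filters operate on one group only. An observed difference could partly reflect admission history, in either direction.

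The size is not known. The range of 2 to 8 points rests wholly on assumed risks and shares, and at 15 versus up to 60 the bias is probably smaller than random error. The conclusion also assumes that an admission in the prior year is a reasonable marker for the high-use group, which the protocol does not define, and that the companion protocol adds no further restriction. This is an inexpensive improvement to an exploratory comparison. It is not a flaw in the pilot's main purpose.

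**What to change.** In Sample Size and Data Analysis, item 2, and in the companion administrative-data protocol if it repeats the list, add one group-matching factor: any psychiatric inpatient admission in the 12 months before the index admission, none versus one or more. If cells become too sparse, coarsen the age or diagnostic groups. Failing that, leave the factor out of the matching and tabulate prior admission by group beside the outcomes.

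Also extend the caveat, for example: *The contrast with administrative controls is open to selection and confounding as well as to imprecision, and a difference in readmission will not by itself be read as an effect of Recovery Bridge.* This is needed even with the extra factor, which does nothing about volunteering or the capacity check.

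Cost: one look-back variable, which may have to be added to the listed data fields and submitted as a modification. A two-level factor doubles the number of possible matching cells, so the control group may end below 60.

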## Sample Size and Data Analysis

**If you uploaded a separate research protocol document in the 'Research Protocol' page, cite the applicable section and page numbers from that document in the answer boxes below.**

1 \* **Provide the rationale and sample size calculations for the proposed target population:**  
Our goal is to collect quantitative and qualitative information on proof of concept through a small scale open pilot trial. We have determined that implementing Recovery Bridge with 15 Veterans and conducting qualitative interviews with all Veteran participants, 2 PS interventionists, and up to five or six key stakeholder will be sufficient to determine feasibility and acceptability. We will also collect administrative data (described in companion protocol HP-00110495-Supplemental Administrative Data Protocol) to create a matched group sample of up to 60 to compare services outcomes. As a open-trial this small pilot is not powered.

2 \* **Provide the plan for data analysis. Include in the description the types of comparisons that are planned (e.g., comparison of means, comparison of proportions, regressions, analysis of variance, etc.), which is the primary comparison/analysis, and how the analyses proposed will relate to the primary purposes of the study:**  
Exploratory Outcomes and Analysis for the Active Sample: The Hope Scale (HS), a twelve-item measure that measures hopefulness (23). Research has found HS scores to be positively associated with goal related activities and coping strategies (24) The WHOQOL-BREF. This brief instrument allows for ratings across 8 quality of life dimension and has strong psychometric properties (25). The Maryland Assessment of Recovery: is a brief self-report measure of recovery orientation and has strong psychometric properties (26). The above scales will be assessed during the inpatient stay (baseline) after the patient has signed consent to participate in the study and after the final session of the Recovery Bridge intervention (follow-up) which will be done over video (Microsoft Teams) or the phone. Exploratory analysis of these measures will primarily be descriptive. Effect sizes (mean change + baseline standard deviation) will be calculated but due to small sample size will have a high standard error, hence will not be used to power a larger study

Exploratory Services Related Outcomes Using Active and Control Sub-Samples.

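### McNemar's test and matched-pairs odds ratios are specified for 15 Veterans against a group-matched sample of up to 60 controls, but the plan forms no pairs

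*Combined protocol and SAP*

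**What the plan says.** Sample Size and Data Analysis, item 2, compares the 15 active Veterans with a "randomly selected contemporaneous (or near-contemporaneous) group-matched sample (n of up to 60) from administrative data" on two yes/no outcomes: meeting the post-discharge engagement metric, and psychiatric readmission within 30 days. On how controls are matched it says only "Matching will be based on diagnostic grouping, age group, and gender". Alongside descriptive proportions by group, "matched pairs analyses (McNemar's test and matched-pairs OR's with 95% confidence intervals) will be used to compare" the two samples. The section adds: "These analyses are exploratory given limited power and precision of 95% confidence intervals".

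Item 1 of the same section describes the comparator in the same way, as data used to "create a matched group sample of up to 60 to compare services outcomes". The administrative data are said to be "described in companion protocol HP-00110495-Supplemental Administrative Data Protocol"; that companion document was not available for this review. No supplied section gives a matching ratio, links an active Veteran to a particular control, or says how several controls per Veteran would be handled.

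**The concern.** Group (frequency) matching makes the distribution of the matching factors similar in the two samples. It links no individuals. McNemar's test and the matched-pairs odds ratio use only the two discordant counts from linked 1:1 pairs, so they cannot be computed from a group-matched sample until someone creates pairs.

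To run the stated test, an analyst would have to choose up to 15 of the controls and assign each to an active Veteran. The three matching factors define cells, not pairs. Where a cell holds several controls, the choice among them is open, and the p-value, odds ratio and interval depend on it. Controls not chosen drop out of the test and its interval, although they remain in the descriptive proportions.

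This is the only between-group inferential analysis in the study, serving the first part of Aim 3.

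**Working it through.** The plan states no power, alpha or event rate for this comparison, so it has no figure of its own to reproduce. Every event rate below is an assumption, as is the two-sided 0.05 level.

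**Inputs from the plan.** Active n = 15; controls up to M = 60; both outcomes binary.

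**1. Structure.** At the ceiling, 60/15 = 4 controls per active Veteran. A 1:1 test uses at most 15, so 60 − 15 = 45 controls (75%) are left out. With c = 0, the exact two-sided p is 2 × 0.5^b: 5 discordant pairs give 0.0625 and 6 give 0.031, so at least 6 pairs, all in one direction, are needed.

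**2. Dependence on the pairing.** Hold the data fixed, with a of 15 active and x of M controls having the event. Choose and pair 15 controls at random, ignoring the matching cells. Let c be the pairs in which only the control has the event and b those in which only the active Veteran has it. Then c ~ Hypergeometric(M, x, 15 − a). Events among the a controls paired with active events follow Hypergeometric(M − (15 − a), x − c, a), and b is a minus that number.

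Worked case, engagement 14/15 vs 36/60:
- One active Veteran is not engaged, so c is 0 with probability 24/60 = 0.40 and 1 with probability 0.60.
- If c = 0, p ≤ 0.05 needs b ≥ 6, which has probability 0.484.
- If c = 1, it needs b ≥ 8 (b = 8 gives p = 20/512 = 0.039; b = 7 gives 18/256 = 0.070), which has probability 0.131.
- Total: 0.40 × 0.484 + 0.60 × 0.131 = 0.272.

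| Active | Controls | Pairings with p ≤ 0.05 | A discordant count is zero | Central 95% of p |
|---|---|---|---|---|
| 14/15 | 36/60 | 27% | 40% | 0.008 to 0.63 |
| 13/15 | 36/60 | 9% | 16% | 0.016 to 1.0 |

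Fisher's exact test on all 75 Veterans gives one answer for each data set: p = 0.015 and p = 0.070. With 18/30 controls engaged, the shares of pairings at p ≤ 0.05 are 24% and 5%.

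**3. Precision.** Under equal proportions, the standard error with 15 controls relative to M controls is √[(1/15 + 1/15)/(1/15 + 1/M)]. This is 1.265 at M = 60 and 1.155 at M = 30, so the interval is 26% or 15% wider.

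**4. Power, for scale only.** Exact McNemar on 15 independent pairs against Fisher on 15 vs 60:
- engagement 85% vs 60%: 16% vs 37%
- engagement 90% vs 50%: 49% vs 86%
- readmission 5% vs 15%: about 1% for both

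**5. Whether a readmission odds ratio exists.** At a common risk r, let q = r(1 − r). With 15 pairs, P(b = 0 or c = 0) = 2(1 − q)^15 − (1 − 2q)^15. For the crude 15 vs 60 table, the probability of a zero cell is 1 − [1 − r^15 − (1 − r)^15][1 − r^60 − (1 − r)^60].

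| Common risk | 3% | 6% | 10% | 15% | 20% | 25% |
|---|---|---|---|---|---|---|
| 15 pairs | 88% | 67% | 44% | 25% | 14% | 9% |
| 15 vs 60 | 69% | 41% | 21% | 9% | 4% | 1% |

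At 6%, 15 pairs are expected to give 15 × 2 × 0.06 × 0.94 = 1.69 discordant pairs.

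**6. A measure that always exists.** For 0/15 vs 4/60 the risk difference is −6.7 points. The Wilson limits are 0 to 20.4% and 2.6% to 15.9%, so the Newcombe interval is −0.067 − √[0² + (0.159 − 0.067)²] = −0.159 to −0.067 + √[0.204² + (0.067 − 0.026)²] = +0.141.

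**The case against.** The best defence is that the design is under-described rather than mismatched. The factors named could be used for individual matching, the ceiling of 60 does not rule out 15 individually matched controls, and the companion protocol may define pairs. If it forms 1:1 pairs, McNemar's test is valid and only the description of the sample is loose. That possibility stands, but the analysis is written in this section, which calls the sample group-matched and then names a paired test. The wording needs correcting on either reading. A ceiling of 60 is also hard to explain if only 15 controls can be tested.

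Two criticisms of the figures are fair. Real pairing would be restricted to cells of the matching factors, so the spread in step 2 is probably too wide; restriction would narrow it without removing the unspecified choice. The engagement examples are also the more sensitive ones. At 12/15 vs 36/60 only about 2% of pairings reach p ≤ 0.05. For plausible readmission counts, such as 1/15 vs 4/60, essentially none do, although the p-value and odds ratio still vary.

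Finally, the pilot claims no power, so lost power matters little. Exploratory status limits the stakes, but it does not make a paired test computable on unpaired data.

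**Conclusion.** The concern holds. The plan specifies a paired analysis for a sample it describes as group-matched, and nothing in the supplied text creates the pairs. This is an analysis that does not fit its stated design, and more than a missing detail.

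The structural point needs no assumed rates: at most 15 pairs, with up to 45 controls excluded. The sizes in steps 2, 4 and 5 rest on assumed event rates. Step 2 also ignores the matching cells, and steps 4 and 5 assume independence within pairs. On those terms, the same engagement data could be reported as significant or not depending on the pairing. For readmission the significance verdict would rarely change, but the paired odds ratio would often be zero, infinite or undefined.

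The point should be fixed before analysis. It does not bear on the feasibility or acceptability conclusions.

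**What to change.** State whether matching is by group or individual, and at what ratio, in agreement with the companion administrative-data protocol. Then align the analysis.

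If matching is by group, replace the sentence on McNemar's test and matched-pairs odds ratios with:

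> For each outcome we will report the proportion in each group and the risk difference with a score-type (Newcombe or Miettinen-Nurminen) 95% confidence interval, using all controls. As a supportive estimate we will report an exact or Mantel-Haenszel analysis stratified by the matching factors. With 15 Veterans the strata will be sparse, and a readmission odds ratio may not be estimable.

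If individual 1:M sets are formed, state M and how sets are built, and use exact conditional logistic regression with the matched set as stratum. With M = 1 this reduces to the exact McNemar test, so a genuine 1:1 design loses nothing.

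The cost is one or two sentences of analysis text, with no extra data or participants. Using all controls makes a non-estimable readmission odds ratio less likely but does not rule it out, which is why the risk difference comes first.
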